3.9.1.5.1 Time to onset of any CTC grade ≥ 2 [≥ 3] event

Time to onset of CTC grade ≥ 2 [≥ 3] event will be summarized using the Kaplan-Meier method. Median time to onset and 95% CI will be provided. In addition, Ascending Kaplan-Meier plots will be generated.

Time to onset of CTC grade ≥ 2 [≥ 3] event is defined as the time from the start of treatment to the start date of the first incidence of an event of CTC grade ≥ 2 [≥ 3] i.e. time in days is calculated as (start date of first occurrence of the event) – (date of first dose of study treatment) +1.

In the absence of an event during the on-treatment period, the censoring date applied will be the earliest of the following dates:

- end date of on-treatment period (end of study treatment + 30 days).
- death date
- start date of new antineoplastic therapy (with the exception of palliative radiotherapy or fulvestrant monotherapy) before experiencing any CTC grade ≥ 2 [≥ 3] event.
- data cut-off date.
- withdrawal of informed consent date

3.9.2 Laboratory data

On analyzing laboratory data, data from all sources (central and local laboratories) will be combined. The summaries will include all laboratory assessments collected no later than 30 days after the last administration of study treatment. All laboratory assessments will be listed and those collected later than 30 days after the last treatment date will be flagged in the listings. If laboratory values are provided as ' $<X$ ' (i.e. below limit of detection) or ' $>X$ ', prior to conversion of laboratory values to SI unit, these numeric values are set to X.

Grade categorization of lab values will be assigned programmatically as per NCI Common Terminology Criteria for Adverse Events (CTCAE) version 4.03. The calculation of laboratory CTC grades will be based on the observed laboratory values only, clinical assessments will not be taken into account. The criteria to assign CTC grades are given in the document "Novartis internal criteria for CTC grading of laboratory parameters". The latest available version of the document based on the underlying CTCAE version 4.03 at the time of analysis will be used.

For laboratory tests where grades are not defined by CTCAE, results will be graded by the low/normal/high classifications based on laboratory normal ranges.

The following summaries will be produced for the laboratory data (by laboratory parameter):

- Worst post-baseline CTC grade (regardless of the baseline status). Each subject will be counted only for the worst grade observed post-baseline
- Shift tables using CTC grades to compare baseline to the worst post-baseline value will be produced for hematology and biochemistry laboratory parameters with CTC grades.
- For laboratory parameters where CTC grades are not defined, shift tables to the worst post-baseline value will be produced using the low/normal/high classifications based on laboratory reference ranges.

3.9.2.1 Blood Glucose parameters

HbA1c, fasting plasma glucose and fasting C-peptide data will be summarized in tables by time point and treatment. Summary statistics include number of patients with available data, mean, standard deviation, median, minimum and maximum. Figures of mean glucose/C-peptide levels

with two-sided 95% confidence intervals over time by treatment may also be produced to view the trends over time.

For plasma glucose only, the following summaries will be provided:

- Time to first occurrence of CTC Grade ≥ 2 hyperglycemia
- Time to first occurrence of CTC Grade ≥ 3 hyperglycemia
- Time to resolution of CTC Grade ≥ 2 hyperglycemia
- Time to resolution of CTC Grade ≥ 3 hyperglycemia

Note that CTC Grade 3 and 4 hyperglycemia events use both fasting and non-fasting plasma glucose laboratory values. Median time to onset, duration and 95% CI will be summarized. In addition, ascending Kaplan-Meier plots will be generated. In addition, median and range of time to event will be summarized.

A plot of baseline HbA1c vs. worst post-baseline HbA1c (%) will be presented.

Time to first occurrence of Grade ≥ 2 [≥ 3] lab event

Time to onset of first grade 2 [≥ 3] or worse toxicity is defined as the time from the start of treatment to the start date of the first incidence of grade 2 [≥ 3] or worse toxicity i.e. time in days is calculated as (start date of first occurrence of grade 2 [≥ 3] or worse toxicity) – (date of first dose of study treatment) +1.

In the absence of grade 2 [≥ 3] or worse toxicity during the on-treatment period, the censoring date will be the earliest date from the following dates: last date of administration of study treatment + 30 days, analysis cut-off date, new anti-cancer therapy start date, death date, withdrawal of informed consent date and last non-missing assessment for the lab parameter if the event is lab based).

Note: patients who have grade 2 [≥ 3] or worse toxicity at the baseline will be excluded from this analysis.

Time to resolution (i.e. duration) of Grade ≥ 2 [≥ 3] lab event

Time (days) to resolution of an event is defined as time from first onset to the date of resolution of the event: (date of resolution of event) – (date of first onset of event) + 1. Resolution of an event means that there is a lab value returning to grade ≤ 1 . The following lab parameters will be analyzed:

- Grade 2 or worse Hyperglycemia
- Grade 3 or worse Hyperglycemia

Time to resolution of an event will be presented for the subset of the Safety Set who experienced the event.

In the absence of a resolution during the on-treatment period, the censoring date is the earliest of the following dates: end of treatment + 30 days, analysis cut-off, new anticancer therapy start date, death date, withdrawal of informed consent date and last non-missing assessment for the lab parameter.

Ascending Kaplan-Meier curves will be constructed by treatment arm. Medians together with 95% confidence intervals will be presented for each treatment arm. 25th percentile and 75th

percentile may be considered as well. In addition, the median and range of time to resolution for patients with an event will also be summarized.

The following listings will be produced for the laboratory data:

- Listing of patients with CTC grade 3 or 4 laboratory abnormalities;
- Listing of all laboratory data with values flagged to show the corresponding CTC grades and the classifications relative to the laboratory reference ranges.
- Urinary parameters for all patients

In order to summarize labs parameters as applicable, collected over time (including unscheduled visits), the assessments will be time-slotted.

Time windows for laboratory parameters

Assessment (1)	Target day of assessment	Time Interval
Baseline		≤ Day 1
Cycle 1 Day 8	8	Day 2 to Day 11
Cycle 1 Day 15	5	Day 12 to Day 18
Cycle 2 Day 1	29	Day 26 to day 35
Cycle 2 Day 15	43	Day 36 to day 49
Cycle 3 Day 1	57	Day 50 to day 70
Cycle 4 Day 1	85	Day 71 to day 98
Cycle k Day 1 ($k \geq 5$)	$=(k-1)*28+1$	Day d-14 to day d+13
End of Treatment		Assessment taken at the EOT visit

(1) HbA1c is measured on-treatment at Cycle 3 Day 1 and EOT and same rule applies.

For laboratory parameters, all scheduled/unscheduled assessments should be assigned to time windows. In case of multiple values per window, the one closest to the planned visit date should be used. If 2 values are equidistant to the planned visit date, the selection should be made by selecting the one assessed by central (if any) and otherwise - for multiple central assessments equidistant to the planned visit - the last value.

Further derivation of laboratory parameters might be required for CTCAE grading. For instance, corrected calcium can be derived using the reported total calcium value and albumin at the same assessment using the following formula:

$$\text{Corrected Calcium (mg/dL)} = \text{Calcium (mg/dL)} - 0.8 [\text{Albumin (g/dL)} - 4]$$

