Investigations (Fasting Plasma Glucose)	
Hyperglycemia (see also Section 6.3.2.1.3)	
	
Always consider consultation with a diabetologist and recommend/reinforce on lifestyle changes as per ADA, i.e. exercise and dietary advice (e.g. small frequent meals, low carb, high fiber, low process food intake, three macronutrient balanced meals and 2 optional small snacks rather than one large meal).
 
Note: this table provides dose management recommendations. The preferred option for treating alpelisib-induced hyperglycemia is metformin, given its wide availability and well characterized safety profile. However, in case of intolerance to or unavailability of metformin, investigator's judgment should be exercised and other insulin sensitizers such as SGLT2 inhibitors, thiazolidinediones or dipeptidyl peptidase-4 Inhibitors can be used.

Grade 1 (> ULN - 160 mg/dL) [> ULN - 8.9 mmol/L] For patients with baseline values between >ULN – 140 mg/dL (ULN – 7.7 mmol/L) this apply only for values > 140 mg/dL (7.7 mmol/L)	
Maintain dose level, and remind patient on lifestyle changes*.
 
 ● If FPG < 140 mg/dl, consider adding metformin as per guidance below or in cooperation with diabetologist ● If FPG 140-160 mg/dl, start/intensify metformin as per guidance below or in cooperation with diabetologist 
Metformin 500 mg once daily with dinner. If no gastrointestinal (GI) intolerance after several days, increase to 500 mg bid, with breakfast and dinner. If tolerated, increase to 500 mg with breakfast, and 1000 mg with dinner. If tolerated, 1000 mg bid with breakfast and dinner. If not tolerated, reduce to prior tolerated dose.
 
Monitor FPG as clinically indicated and at least weekly for 8 weeks, then continue checking at least every two weeks until FPG is within baseline values.

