Grade 3 (FPG > 250 - 500 mg/dL) [> 13.9 - 27.8 mmol/L]	
Omit alpelisib/placebo and confirm fasting status of the assessment. If non-fasting, re-check within 24 hours.
 
Regardless of fasting status, consider IV fluids if symptoms of hyperglycemia or signs of volume depletion.
 
Exclude confounding factors like e.g. urinary tract infection and consider consultation with a diabetologist.
 
Administer intravenous hydration and intervention for electrolyte/ketoacidosis/hyperosmolar disturbances as clinically appropriate. Start metformin and titrate as outlined for Grade 2, add insulin sensitizers (i.e. pioglitazone) or a SGLT2 inhibitor, if available, as outlined for Grade 2. Insulin may be used for 1-2 days until hyperglycemia resolves, however this may not be necessary in the majority of alpelisib-induced hyperglycemia given the short half-life of alpelisib.
 
Monitor FPG as clinically indicated and at least twice weekly until FPG resolves to \leq Grade 1.
 
 • If FPG resolves to \leq 160 mg/dL within 3-5 days, while off study treatment and on metformin, re-start alpelisib/placebo and reduce 1 dose level, continue with anti-diabetic treatment..A second and third oral hypoglycemic agent may be initiated concomitantly, if needed, in consultation with a diabetologist. Check FPG at least weekly for 8 weeks, then continue checking at least every 2 weeks, alert treating physician if FPG>250mg/dl • If FPG does not resolve to \leq 160 mg/dL within 3-5 days while off study treatment and on metformin, consult a diabetologist for management of diabetes is strongly recommended. • If FPG does not resolve to \leq 160 mg/dL within 21 days after institution of appropriate anti-diabetic treatment in cooperation with diabetologist and exclusion of confounding factors e.g. urinary tract infection, permanently discontinue patient from alpelisib/placebo treatment.

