10.5.3.3 Laboratory abnormalities

For laboratory tests covered by the CTCAE version 4.03, the study's biostatistical and reporting team will grade laboratory data accordingly. For laboratory tests covered by CTCAE, a Grade 0 will be assigned for all non-missing values not graded as 1 or higher. Grade 5 will not be used.

For laboratory tests where grades are not defined by CTCAE, results will be graded by the low/normal/high classifications based on laboratory normal ranges.

The following by-treatment summaries will be generated separately for hematology, biochemistry and urinary laboratory tests:

- Number and percentage of patients with worst post-baseline CTC grade (regardless of the baseline status)
- shift tables using CTCAE grades to compare baseline to the worst on-treatment value
- for laboratory tests where CTCAE grades are not defined, shift tables using the low/normal/high/(low and high) classification to compare baseline to the worst on-treatment value.
- listing of all laboratory data with values flagged to show the corresponding CTCAE grades and the classifications relative to the laboratory normal ranges.
- listing of all notable laboratory abnormalities (i.e., newly occurring CTCAE grade 3 or 4 laboratory toxicities)

In addition to the above mentioned tables and listings, [REDACTED], for example [REDACTED]

be specified in the statistical analysis plan.

Laboratory values collected later than 30 days after study treatment discontinuation will be flagged in the listings.

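### Time to resolution of hyperglycemia can end on a non-fasting glucose of 161-250 mg/dL, which is no evidence of a return to Grade 1 or lower

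*SAP*

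**What the plan says.** SAP 3.9.2.1 plans time to first occurrence and time to resolution of plasma-glucose hyperglycemia at two thresholds, Grade 2 or worse and Grade 3 or worse. Time to resolution runs from first onset to the resolution date, plus one day. On what counts as resolution it says: "Resolution of an event means that there is a lab value returning to grade" 1 or lower. Nothing there restricts the value to a fasting sample or asks for a second one.

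On the values used for grading, the same section adds: "Note that CTC Grade 3 and 4 hyperglycemia events use both fasting and non-fasting plasma glucose laboratory values". Grades 1 and 2 are not mentioned.

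Protocol 10.5.3.3 supplies a default for laboratory tests that CTCAE covers: "a Grade 0 will be assigned for all non-missing values not graded as 1 or higher". Protocol Table 6-3 sets its glucose grades under a fasting plasma glucose heading. It also foresees non-fasting results, telling the site in the Grade 3 and Grade 4 rows to "confirm fasting status of the assessment. If non-fasting, re-check within 24 hours".

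SAP 3.9.2 pools central and local laboratory results and refers the CTC grading criteria to a sponsor-internal document that is not part of the supplied plan.

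**The concern.** The grading text and the resolution text do not fit together for a non-fasting glucose above 160 and up to 250 mg/dL. It is too low for Grade 3, and it appears not to be eligible for Grade 1 or 2, because only Grades 3 and 4 are said to use non-fasting samples. The protocol's default then makes it Grade 0. Grade 0 satisfies the resolution rule, so the event closes on a value that says nothing about whether fasting glucose has come back to 160 mg/dL or lower. The gap affects both thresholds.

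Protocol 1.2.2.2 names hyperglycemia among the most common adverse events with alpelisib, it is the first grouping in the special-interest table of SAP 3.9.1.5, and SAP Amendment 4 added these onset and resolution analyses for it. Protocol 6.3.2.1.3 describes the event as generally manageable. Duration bears directly on that description, so a rule that can only shorten it deserves correction.

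**Working it through.** The documents give no figure for time to resolution, so there is nothing to reproduce. The check is to apply the written rules.

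**Inputs**
- Cut-offs in mg/dL (Protocol Table 6-3): Grade 1, above ULN to 160; Grade 2, above 160 to 250; Grade 3, above 250 to 500; Grade 4, above 500.
- Non-fasting values count for Grades 3 and 4 (SAP 3.9.2.1). That Grades 1 and 2 are fasting-only is an inference from this note and from the heading in Table 6-3.
- Default of Grade 0 (Protocol 10.5.3.3).
- Resolution is any value of Grade 1 or lower; duration = resolution date - first onset date + 1 (SAP 3.9.2.1).
- Assumption: ULN = 100 mg/dL. It decides only whether 150 is Grade 1 or Grade 0, and both count as resolved.

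**Step 1: grade the same number both ways**

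| Glucose (mg/dL) | Fasting | Non-fasting |
|---|---|---|
| 150 | Grade 1, resolved | Grade 0, resolved |
| 161 | Grade 2, not resolved | Grade 0, resolved |
| 200 | Grade 2, not resolved | Grade 0, resolved |
| 250 | Grade 2, not resolved | Grade 0, resolved |
| 251 | Grade 3, not resolved | Grade 3, not resolved |

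The anomaly is confined to non-fasting values of 161-250 mg/dL.

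**Step 2: direction**

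The resolution date is the earliest qualifying value after onset. Adding values to the qualifying set can bring that date forward or turn a censored event into a resolved one. It cannot move the date back. The effect on time to resolution is therefore towards shorter, whatever its size.

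**Step 3: mechanics on an invented sequence**

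Fasting 300 on day 15, non-fasting 210 on day 18, fasting 280 on day 22, fasting 190 on day 29, fasting 150 on day 43.
- Non-fasting 210 scored Grade 0: 18 - 15 + 1 = 4 days.
- Non-fasting 210 left ungraded, or graded by the fasting cut-offs: 43 - 15 + 1 = 29 days.

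The result is the same at both thresholds. The sequence shows how the rule works and does not estimate its effect. The checks are sparser than Table 6-3 requires after a Grade 3 event, so the size of the gap has no meaning for the trial.

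**Step 4: separate the single-value question**

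All fasting: 300 (day 15), 158 (day 22), 270 (day 29), 260 (day 36), 150 (day 43), 140 (day 57). Duration is 22 - 15 + 1 = 8 days under every treatment of non-fasting values, although a Grade 3 value recurs on day 29. If the next fasting value had to agree, resolution would fall on day 43: 43 - 15 + 1 = 29 days. Restricting resolution to fasting values does not change this case; only a confirmed definition does.

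**The case against.** The strongest objection is that the Grade 0 step joins a note about Grades 3 and 4 to a general protocol sentence that the SAP laboratory section does not repeat, while the grading criteria that govern sit in a document nobody outside the sponsor can read. That document may leave non-fasting values ungraded or handle them as a separate parameter. This stands, and it is why the point is that the rule can end an event this way. It does not remove the need to act, since neither document says how such values are handled for resolution.

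A second objection is that scheduled glucose is fasting, that Table 6-3 requires FPG at least twice weekly after a Grade 3 event until Grade 1 or lower, and that a non-fasting sample at Grade 3 or 4 calls for a re-check within 24 hours. Non-fasting values of 161-250 mg/dL may therefore be few. That also stands: frequency cannot be derived. But unscheduled local tests are allowed (Protocol 7.2.2.5) and are pooled, so such values can reach the analysis.

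Third, a single return below a threshold is a clear definition, and requiring confirmation is a choice on which statisticians differ, because it would confirm resolution but not onset. This succeeds against making confirmation mandatory. A reader might go further and infer that measurement noise alone produces many false resolutions. That depends on how close the true value lies to 160. With constant true glucose G, lognormal error and eight checks, the chance of at least one value at or below 160 is 1 - (1 - p)^8, where p = Φ(ln(160/G)/CV). At an assumed CV of 10%, G = 170 gives p = 0.272 and 92%; G = 200 gives p = 0.013 and about 10%; G = 255 gives p below 0.00001 and effectively zero. The documents supply neither the CV nor the distribution of G, so no overall percentage can be defended, and noise is irrelevant while glucose stays at Grade 3 level.

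Finally, the summary is descriptive and sits beside glucose and HbA1c over time and a full listing of graded laboratory values, so odd early resolutions would be traceable. That limits the consequence but does not correct the reported median.

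**Conclusion.** The point holds as a defect in the written rule. On the supplied text, one non-fasting glucose of 161-250 mg/dL can close a Grade 2 or worse or Grade 3 or worse event although it gives no evidence of a return to Grade 1 or lower, and the bias in time to resolution is towards shorter. This rests on reading Grades 1 and 2 as fasting-only and on the protocol's Grade 0 default applying to these values. The size is unknown.

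A reader might infer that unresolved Grade 3 hyperglycemia is being recorded as resolved. The documents do not support that. A non-fasting 161-250 mg/dL does not show that fasting glucose is still above 160; the patient may or may not have resolved. The fault is that the value is uninformative and is nevertheless counted.

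The matter concerns a descriptive safety summary. Efficacy analyses and trial decisions are unaffected.

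**What to change.** In SAP 3.9.2.1, state that resolution is the first fasting plasma glucose of Grade 1 or lower after onset. State also that non-fasting values not reaching Grade 3 or 4 are treated as ungraded for this analysis, are not set to Grade 0, and are not used to establish resolution. Check the internal grading criteria for consistency with this wording. Optionally, report confirmed resolution, with the next fasting value also Grade 1 or lower, as a sensitivity analysis.

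The cost is wording and programming. Protocol 7.2.2.5.3 already has fasting status captured in the CRF, so no new data are needed. The small downside is that some events will resolve slightly later, or be censored, when only non-fasting values follow. That includes non-fasting values of 160 mg/dL or lower, which would no longer count.

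### SAP 3.9.2.1 laboratory windows leave days 19–25 unassigned and print a Cycle 1 Day 15 target of day 5, outside its own window; only by-visit summaries are affected

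*SAP*

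**What the plan says.** SAP 3.9.2.1 contains an untitled-number table of time windows for laboratory parameters. It is introduced by the statement that, to summarise parameters "collected over time (including unscheduled visits), the assessments will be time-slotted". The row at issue reads "Cycle 1 Day 15 5 Day 12 to Day 18": visit, target day, and the interval "Day 12 to Day 18". The next two rows are Cycle 2 Day 1, target 29, "Day 26 to day 35", and Cycle 2 Day 15, target 43, "Day 36 to day 49".

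Below the table the SAP states that "all scheduled/unscheduled assessments should be assigned to time windows". It then gives the selection rule: "In case of multiple values per window, the one closest to the planned visit date should be used". Equidistant values are resolved in favour of the central laboratory, and otherwise in favour of the last value.

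The windows feed the by-time-point summaries. Earlier in SAP 3.9.2.1, HbA1c, fasting plasma glucose (FPG) and fasting C-peptide are to be tabulated by time point and treatment, with optional plots of mean glucose and C-peptide over time. SAP 3.9.2 combines central and local laboratory results.

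The protocol schedules FPG on Days 8 and 15 of Cycle 1, Days 1 and 15 of Cycle 2, and Day 1 of each later cycle (7.2.2.5.3), with ±3 days allowed (7.2.2.5). For Grade 1 hyperglycaemia, Protocol Table 6-3 adds: "Monitor FPG as clinically indicated and at least weekly for 8 weeks". Grade 2 is also checked at least weekly, and Grade 3 at least twice weekly until it resolves.

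**The concern.** A window table has to be exhaustive if every assessment is to be assigned to it. This one is not, so two programmers following the SAP could treat a Day 22 sample differently: one leaves it out, the other forces it into an adjoining visit. A target that lies outside its own window makes the closest-value rule ambiguous in the same way.

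The days concerned fall in the first month, when the protocol says alpelisib-induced hyperglycaemia typically appears (6.3.2.1.3). The Table 6-3 monitoring rules make unscheduled samples on days 19–25 foreseeable, and Protocol 7.2.2.5 brings local results into the eCRF when they drove a treatment decision or when no concomitant central result exists. At stake is whether the early by-visit glucose summaries can be reproduced from the SAP, and whether they use every value they are entitled to use.

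**Working it through.** **Inputs.** Targets and intervals from the SAP 3.9.2.1 table: C1D8, target 8, Day 2–11; C1D15, target 5, Day 12–18; C2D1, target 29, Day 26–35; C2D15, target 43, Day 36–49; C3D1, target 57, Day 50–70; C4D1, target 85, Day 71–98; CkD1 for k ≥ 5, target d = (k−1)×28+1, Day d−14 to d+13.

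**Target check.** Nominal study day = (cycle−1)×28 + day of cycle, which agrees with the table's own formula for k ≥ 5. For C1D15 this gives (1−1)×28+15 = 15, the centre of Day 12–18. The targets 8, 29, 43, 57, 85 and (k−1)×28+1 all lie inside their windows. The printed 5 does not; it lies in the C1D8 window.

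**Coverage check.** Listing every day from Day 2 to Day 294 (the end of the C11D1 window) against the intervals leaves exactly seven days in no window: 19, 20, 21, 22, 23, 24 and 25. No day is in two windows.

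**Who is affected by the gap.** With ±3 days, an on-schedule C1D15 sample falls on Day 12–18 and an on-schedule C2D1 sample on Day 26–32. Both ranges are already covered. If the gap were closed at Day 22:

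- Days 19–21 would be 4, 5 and 6 days from target 15.
- Days 22–25 would be 7, 6, 5 and 4 days from target 29.
- An on-schedule sample is at most 3 days from its target, so it would always be chosen over a gap-day sample.

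Closing the gap therefore changes a by-visit summary only for a patient with no on-schedule sample at the adjoining visit.

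**Selection within Day 12–18.** Distances for days 12 to 18 are:

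| Target | 12 | 13 | 14 | 15 | 16 | 17 | 18 |
|---|---|---|---|---|---|---|---|
| 5 | 7 | 8 | 9 | 10 | 11 | 12 | 13 |
| 15 | 3 | 2 | 1 | 0 | 1 | 2 | 3 |

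With target 5 the earliest value always wins, for example Day 12 (distance 7) over Day 15 (distance 10). Of the 21 possible pairs of distinct days in the window, the choice differs between the two targets in 12 if ties go to the later value, or in 9 if the three pairs tied under target 15 (12/18, 13/17, 14/16) are set aside.

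**Convention for closing the gap.** Midpoints between successive targets are (29+43)/2 = 36, (43+57)/2 = 50, (57+85)/2 = 71 and (85+113)/2 = 99. In each case the midpoint day is the first day of the later window. Applied to 15 and 29, the midpoint is 22, so C1D15 would end on Day 21 and C2D1 would start on Day 22. The boundary between C1D8 and C1D15, (8+15)/2 = 11.5, already agrees with the existing Day 11/Day 12 split and supports 15 as the intended target.

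**The case against.** The strongest reply is that almost nothing changes. Scheduled samples are covered, and one value per window is used, so an extra Day 22 test in a patient who also attended Cycle 2 Day 1 on time would be passed over with or without the gap. That is correct. It rules out a reading a colleague might reach: that the gap discards the weekly monitoring values of hyperglycaemic patients and so biases early glucose means selectively in the alpelisib arm. What sets those extra values aside is mainly the one-value-per-window rule, not the gap. The documents do not say how many patients lack an on-schedule sample, or in which arm.

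A second reply concerns the target. The selection rule refers to the planned visit date, which for this row is Cycle 1 Day 15, and a target of 5 is impossible on its face. A digit may have been lost in the SAP or in reading the PDF. This also stands: it cannot be asserted that the wrong sample will be chosen. That outcome needs literal use of 5 together with two or more values on different days within Day 12–18. The gap does not depend on the doubtful digit.

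A third reply is that the main hyperglycaemia outputs do not use these windows. This too is right. Worst post-baseline grade and shift tables (SAP 3.9.2), time to first occurrence and time to resolution (3.9.2.1), adverse-event-of-special-interest summaries (3.9.1.5) and the laboratory listings are unaffected.

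What survives all three replies is that the SAP requires every assessment to be assigned and gives a table under which seven days cannot be.

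**Conclusion.** The point holds as an internal contradiction in a stated analysis rule, with a small expected effect. Days 19–25 have no window despite the instruction that all assessments receive one. A patient whose only sample near Cycle 1 Day 15 or Cycle 2 Day 1 was drawn on those days is absent from that by-visit summary. The printed target of 5 is inconsistent with its own row; if it is in the source and is used literally, the earliest of several values in Day 12–18 is selected.

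The consequence is limited to descriptive by-time-point tables and the optional mean plots. No test, efficacy conclusion, worst-grade table, shift table, time-to-event output or listing depends on it. Seven unassigned days is a count of calendar days, not an effect size; the shift in any mean cannot be computed from the documents. The conclusion about the gap rests on the limits 18 and 26 being as printed. The conclusion about the target is conditional on the digit being wrong in the SAP itself.

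**What to change.** Check the source table and confirm or set the Cycle 1 Day 15 target at 15. Make the windows contiguous by the midpoint convention the table already follows: Cycle 1 Day 15 = Day 12–21 and Cycle 2 Day 1 = Day 22–35. This changes three cells (one target and two intervals) and the matching programming specification. Any by-visit laboratory outputs already produced should be checked to see which target and which handling of days 19–25 were used. No data collection, visit schedule or clinical rule changes.
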